- A reference (control) TEWL measurement will be taken from intact skin at an anatomically matched site. For example, if the healed wound is on the right foot, we will also measure the same location on the left foot, for comparison.
- Room humidity and temperature readings monitored on the instrument are also recorded.

If the wound has **not healed** by the end of the 16-week timeline, this visit will mark the participant's Final Study Visit and the following information will be collected:

- Wound data (etiology, size, location, duration, wound care modality, determination of presence of callus) will be recorded.
- A digital photograph of the wound will be taken.
- Quality of Life questionnaires such as the SF-12 Health survey, Visual Analogue Pain scale, and Cardiff wound impact questionnaire.

5.2) **Phase B**

The participant will be seen again following wound closure for follow-up assessment of the healed wound over 12 weeks. There will be visits at 2 and 12 weeks (+/-2 weeks) following Study Visit 2 marking wound closure. These visits will last about 1 hour. Participants will be asked to refrain from using any topical product(s) (lotion, study product, ointments, etc.) the day of the study visits.

5.2a) Study Visit 3 (Post-closure, Week 2 +/- 2 weeks)

At two weeks following Study Visit 2, the patient will be asked to return to the clinic to complete Study Visit 3 and begin Phase B of the study. This visit will last about 1 hour. The participant will be asked to refrain from using any topical product(s) (lotion, ointments, etc.) the day of the study visits. The following study activities will take place during this visit:

- Digital photos of the wound site will be taken.
- Wound site evaluation for signs of recurrence and callus determination, including the date of wound healing will be obtained.
- Medication review and adverse event review will be completed.
- Various labs that have been drawn per Standard of Care since enrollment, medication review, and any adverse events will be recorded.
 - For Trans Epidermal water loss (TEWL) measurements (can be collected using noninvasive devices such as Dermalab or GPSKIN, for example):
 - The TEWL probe will be placed on the skin.
 - The TEWL measurement takes approximately five-ten minutes.

- There will be multiple measurements obtained over the healed wound site.

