- A reference (control) TEWL measurement will be taken from intact skin at an anatomically matched site. For example, if your healed wound is on your right foot, we will also measure the same location on your left foot, for comparison.
- Room humidity and temperature readings monitored on the instrument are also recorded.
- Any relevant lab values collected per standard of care (SoC) since enrollment will be captured and recorded.

In addition to the activities completed during this study visit, research staff will complete weekly phone calls to the participant or caretaker to monitor that the wound remains closed during Phase B of the study.

If the patient's wound has **reopened or recurred** within the 2 week timeline this visit will mark the participant's Final Study Visit and the following study activities will take place:

- Digital photos of the wound site will be taken.
- Wound site evaluation for signs of recurrence and callus determination, including the date of wound healing will be obtained. You will receive weekly phone calls for wound site evaluation.
- Quality of life questionnaires such as the SF-12 Health survey, Visual Analogue Pain scale, and Cardiff wound impact questionnaire.

5.2 b) Study Visit 4 (Post-closure, Week 12 +/- 2 weeks)

Study Visit 4 will take place at 12 weeks following wound closure (+/- 2 weeks) in which the patient will be required to travel back to clinic to complete the study activities. The following study activities will take place at Study Visit 4:

- Digital photos of the wound site will be taken.
- Wound site evaluation will be completed.
- TEWL measurements will be obtained using a TEWL probe as previously described.
- Medication review and adverse event review will be completed.
- Any lab values collected per standard of care (SoC) since enrollment will be captured and recorded.
- Quality of Life questionnaires such as the SF-12 Health survey, Visual Analogue Pain scale, and Cardiff wound impact questionnaire and diabetic foot scale questionnaire.

If the patient's wound **recurred or reopened** during the 12 week timeline this visit will mark the participant's Final Study Visit and the following study activities will take place

- Wound data (etiology, size, location, duration, wound care modality, determination of presence of callus) will be recorded.
- A digital photograph of the wound will be taken.

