The proposed research aims to uncover novel mechanisms that compromise closure of chronic diabetic wounds in a general population. Knowledge gained from the proposed study has the potential of providing considerable benefits to wound care by identifying a key player that influences the closure of diabetic wounds. Studies in humans in tandem with previous porcine models will help validate the model for additional studies.

7) Payment

The payment schedule for participants will be different depending on what specific cohort of the study they are enrolled in and will vary by the sites and institutional policies. The site consent will have detailed information regarding the payments for each cohort and each study visit.

Compensation will only be given to participants after the completion of all study visit activities. By law, payments to participants over \$600 per year are considered taxable income.

8) Statistical Analysis

Statistical power and required sample size are estimated for a multivariable linear regression of a continuous outcome variable (TEWL=Y) with a binary predictor variable (biofilm infection) with an expectation of achieving 80% power assuming conditional (fixed X's) model. TEWL measurement at closure visit 2 is used in the analysis to capture the peak TEWL level, to account for wound closure without complete skin barrier function restoration. The regression model assumes that the conditional expectation of Y is estimated given the realized values of X's. The method of sample size calculation uses the squared multiple correlation coefficient, R^2 as a function of Cohen's effect size. With 0.05 level of significance (Type I error) to detect a small (f-square=0.02) to medium (0.15) and large (0.35) difference in mean TEWL between biofilm infected and non-biofilm infected DFU with 10 additional variables controlled in the model will require an effective sample size of 395 participants. Conservatively, we assumed the effect size to be within small and medium values, equal to 0.03. With these parameters we estimate an effective sample size of 264 participants in. Assuming 20% loss to follow-up, we need at least 330 participants to be enrolled in the study. Because Study Aim 3.0 needs larger sample, we will enroll more than 330 participants (N=405) for Aims 1-3.

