Interim Analysis: A blinded interim analysis will be done at 25% and 50% of enrollment. The PIs will be blinded from the interim analysis to maintain the validity and integrity of the study. The purpose of the interim analysis is to inform us the effectiveness of program-related resources and activities that will help the study team get informed decisions regarding modifications, if any, in logistical, monitoring and recruitment procedures.

9.1) Data Collection, Analysis and Management

Clinical data will be recorded in **REDCap (Research Electronic Data Capture (HIPAA compliant))** as clinical research database at IU. Effective Nov 01, 2023, the Redcap database will be transferred to the University of Pittsburgh under [name] oversight. All data collected from all sites within this project will continue to be housed within this central database. Prior to being given access to the data, HIPAA and human subjects certified study staff will be trained in the collection of patient-reported outcomes. Study data will be collected using Standardized **Case Report Forms (CRFs)**, with clear, uniform instructions for study staff. Researcher's access to files will be governed by institutional secure data access policies. Effective November 01, 2023, the REDCap platform will be transferred and operated by the University of Pittsburgh Clinical Research team.

9.2) Data Quality and Security

The study team will review all CRFs. All incoming data will be monitored, with particular attention to: **1)** enrollment and follow-up reports as entered into the database, **2)** potential adverse events, and **3)** missing data or extreme values. Regular reporting to the study team will work to reconcile or report issues as needed and to monitor participant retention. To ensure quality, 10% of the study medical records will be re-abstracted. If the error rate is found to be >5%, staff will be retrained and more extensive data quality checks will take place, with full on-site audit. Study data integrity, adverse events, and design considerations will be reported at all scheduled OSMB. The clinical database administrator will perform quality control assessments for data completeness (missing data) and accuracy (variable range checks, and within and between data field checks) to identify data that appear inconsistent, incomplete, or inaccurate.

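### Nothing in the protocol keeps those who judge ulcer recurrence from knowing the TEWL values that are the Aim 3 exposure

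*Protocol*

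**What the plan says.** **Exposure and outcome.** Aim 3 (Protocol, section 2) relates deficient barrier function at the closed ulcer to recurrence. Section 1 gives the expected direction: pilot work in which closed ulcers with a poor barrier recurred more often.

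**When TEWL is read.** An operator takes TEWL with a probe at Visit 2 (5.1b), Visit 3 (5.2a) and Visit 4 (5.2b). At Visits 2 and 3 the text specifies several readings over the healed site and a reference reading on matched intact skin; Visit 4 refers back to this.

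**How recurrence is judged.** At Visit 3: "Wound site evaluation for signs of recurrence and callus determination, including the date of wound healing will be obtained". Visit 4 asks only for a wound site evaluation. Between visits, "research staff will complete weekly phone calls to the participant or caretaker to monitor that the wound remains closed". No criteria for recurrence, no named assessor and no masked reading of the photographs are given. A recurrence found at Visit 3 makes that visit the participant's last.

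**Blinding.** The one blinding sentence is in section 8, on the interim analysis: "The PIs will be blinded from the interim analysis to maintain the validity and integrity of the study". The note that participants do not receive test results stands under the PeriCam sub-study and does not cover staff. The access rules in 5.3, 9.1 and 9.2 concern privacy and data security.

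**Aim 2.** The exposure is biofilm infection at the initial visit, assessed on debrided tissue. The outcome is TEWL at Visit 2 (section 8).

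**The concern.** The study is observational, so its Aim 3 result is only as good as the independence with which exposure and outcome are recorded. The exposure is obtained in the clinic before the outcome is judged. A member of staff who saw a high Visit 2 reading, with the reference reading beside it, knows which way the hypothesis points for that participant. Callus, a fissure or a small breakdown can be called either way, and the protocol gives no rule to settle it. If such calls lean with TEWL, an association can appear or grow without any true effect. A recurrence call at Visit 3 also ends follow-up, so a swayed early call is not tested at Visit 4.

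Who sees which result, and in what order data are entered, is study conduct. A statistical analysis plan written later cannot mask an assessment already made.

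**Working it through.** **1. The plan's own sample size.** It is not in dispute and masking would not change it. Section 8 gives 80% power, a 0.05 level, 10 covariates plus the biofilm term, and "Conservatively, we assumed the effect size to be within small and medium values, equal to 0.03". The test of one coefficient uses a noncentral F distribution with 1 and N − 12 degrees of freedom and noncentrality f² × N.
- f² = 0.03: N = 264, power 0.8005. This matches.
- f² = 0.02: N = 395, power 0.8006. This matches.
- 264 / (1 − 0.20) = 330. This matches.

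**2. Order of events for Aim 3.**

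| Step | TEWL (exposure) | Recurrence (outcome) |
|---|---|---|
| Visit 2, closure | read in clinic | – |
| Weekly calls | Visit 2 value exists | asked about by research staff |
| Visit 3 | read in clinic | judged on site, listed before TEWL |
| Visit 4 | read in clinic | judged on site, listed before TEWL |

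At every point where recurrence is judged, at least one TEWL value already exists. No text keeps it from the person judging.

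**3. How much this could matter for Aim 3 (illustration).** The protocol gives no closure rate, recurrence rate or TEWL cut-off, so these inputs are assumptions: 50% of retained participants close, a split at median TEWL, and true recurrence of 15% in both halves.
- Closed ulcers: 405 × 0.80 × 0.50 = 162, or 81 per half.
- Three points moved each way gives 18% versus 12%. Apparent odds ratio: (0.18/0.82) / (0.12/0.88) = 1.61.
- Standard error: √[(0.18 × 0.82 + 0.12 × 0.88)/81] = 0.0559, and 0.06/0.0559 = 1.07. False-positive rate: Φ(1.07 − 1.96) + Φ(−1.07 − 1.96) ≈ 19%. A simulation of the two-proportion test with 20,000 replicates gives 18.0%, against 4.8% with no shift.
- 20% versus 12%: odds ratio 1.83, false-positive rate 28.3% by simulation.
- One-sided shift, 18% versus 15%: standard error √[(0.18 × 0.82 + 0.15 × 0.85)/81] = 0.0583, ratio 0.51, false-positive rate about 8%.

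With 132 per group (264/2) and true recurrence of 20% to 30% in both groups, over-calling in the high-TEWL group alone gives:

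| Over-call | False-positive rate |
|---|---|
| 2 points | about 6–7% |
| 5 points | about 14–16% |
| 10 points | about 40–47% |

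**4. Aim 2 (illustration).** If half the ulcers have biofilm, f² = 0.03 is a mean difference of √(0.03/0.25) = 0.35 residual SD. With no true effect and N = 264, a systematic shift of 0.10 SD in TEWL between groups has f² = 0.10² × 0.25 = 0.0025 and gives a false-positive rate of about 13%. A shift of 0.05 SD gives about 7%.

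**The case against.** **Silence is not evidence of exposure.** No text says that one person both takes TEWL and calls recurrence, or that staff consult earlier values. This stands as a limit: the point is a missing safeguard, not a shown breach.

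**Aim 2 is much weaker.** A reader might infer that sites know biofilm status when they place the probe, so that the Aim 2 result is equally at risk. The documents do not support that. Biofilm is read by research methods (electron microscopy, wheat germ agglutinin), and no release of results to sites is described. TEWL is an instrument reading with a reference site and recorded room conditions. The TEWL SOP mentioned in the exclusion criteria, and the case report form instructions in 9.1, may govern which reading counts. Probe placement and multiple readings leave some room for influence, no more.

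**The listed order already helps.** At Visits 3 and 4 the wound evaluation is listed before TEWL, and the activities listed for a recurred wound do not include TEWL. This largely answers the worry about same-visit readings, although the order is not made binding. Knowledge of earlier readings, chiefly Visit 2, remains.

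**The damage can be partly checked later.** A reader might infer that the bias could never be corrected. That goes too far: photographs are taken at Visits 2, 3 and 4, including where the wound has recurred, so a masked re-reading is possible for wounds open at a visit. It cannot recover what was decided on a call, and no re-reading is planned in the protocol.

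**The bias sizes are assumed.** Moving 15% to 18% and 12% adds one fifth of the recurrences in one half and removes one fifth in the other, despite weekly calls. Smaller or one-sided shifts do far less. This stands, and the figures show sensitivity only.

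**Conclusion.** The concern holds for Aim 3. As written, the plan lets recurrence, a judgement without stated criteria, be called by people who can know the TEWL values it will be tested against, and its only blinding sentence does not reach them. The change is worth making because it is cheap and no later analysis can replace it.

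The size cannot be fixed from the documents. Under the assumptions shown, the false-positive rate runs from about 6% for a small one-sided shift, through about 18% for 18% versus 12% with 81 per half, to 40–47% for a 10-point over-call with 132 per group. None of these is an estimate of actual bias.

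Aim 2 is secondary. The protocol's text does not establish that biofilm results influence TEWL readings. The sample size figures reproduce and are unaffected.

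**What to change.** Add one paragraph to section 5.2, with a matching line in 9.1:

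1. At Visits 3 and 4, recurrence (yes/no and date) is entered and locked in REDCap before the TEWL probe is used. This makes the listed order binding.
2. The TEWL form is restricted so that whoever calls recurrence, including staff who make the weekly calls, does not see earlier values. Where possible, that person is not the one who took the readings.
3. Research biofilm assay results stay with the laboratory until database lock. Standard-of-care cultures are not affected.

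The cost is REDCap permissions and a protocol paragraph, with no extra staff or visits. Section 5.3a describes the TEWL device as for research only, with no diagnostic or treatment use, so by the protocol's own account withholding its values takes nothing from care.

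Masking will be partial. Someone who took the Visit 2 reading may recall it, and swab cultures or infection history held at the site may hint at biofilm status, so masking to biofilm should not be described as complete. The rule covers only visits still to come (the protocol is at version 4, and two earlier site groups have closed). Record which visits were masked so that the two periods can be told apart. A masked re-reading of visit photographs can serve as a check for wounds open at a visit.

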This study rests on DFU-patient based findings from a NIDDK-DIACOMP funded pilot study ([name]/[name]) showing that closed DFU with deficient barrier function are more likely to recur. Biofilm infection as assessed through scanning electron microscopy and wheat germ agglutinin assay performed on debrided tissue causes faulty re-epithelialization, compromising skin barrier function at the closed wound site. Such defects are caused by biofilm-inducible miRs which silence junctional proteins necessary for skin barrier function. The IRB protocol associated with this study, rests on our novel patient-based observation that in wound-edge tissue catenin delta1/p120 catenin (CTNND1) is suppressed as measured through immunohistochemistry. CTNND1 is an essential regulator of E-cadherin stability which is regarded as a master organizer in epithelial phenotype and plays a critical role in maintaining the barrier integrity of skin. Our prior study identified miR-9 is a biofilm induced microRNA that targets adherens junction protein E-cadherin. We propose that miR-9 can target CTNND1 (Aim 1). The validation of miR targeting will be performed quantitative real time PCR, Western blot analyses, Argonaute 2 pull down assay and on bead assay. Thus, this proposal, fully based on the study of DFU patients, seeks to conduct a fully powered clinical study testing whether DFU with a history of biofilm infection closes with deficient barrier function (Aim 2). Aim 3 tests whether such functionally deficient wound closure, manifested as high TEWL, is associated with greater wound recurrence. Per FDA, the significance of association studies is heightened by support of a well-founded biological rationale provided by mechanistic studies²². This proposal rests on such mechanisms that have been reported by us in pre-clinical large animal studies¹⁸⁻²⁰. The primary parent study will address

molecular mechanisms implicated in biofilm-induced loss of skin epithelial barrier integrity in DFU patients.

2) Objective

The multi-site parent study will address the following three specific aims:

- Aim 1:** Determine how biofilm induced DFU tissue microRNAs disrupt barrier function of the repairing DFU.
- Aim 2:** Test the incidence of wound biofilm infection at initial visit and test its association with deficient skin barrier function at the closed DFU-site.
- Aim 3:** Test whether closed DFU with deficient barrier function is associated with higher rate of recidivism.

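### Section 8 inflates the sample size for loss to follow-up only, although the powered TEWL outcome exists only for ulcers that close within 16 weeks; the stated minimum of 330 therefore does not give 80% power unless every retained ulcer closes

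*Protocol*

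**What the plan says.** Participants enrol with an open ulcer (protocol section 3.1). Aim 2 concerns barrier function at the site once it has closed (section 2). Section 8 fixes the outcome of the powered regression: "TEWL measurement at closure visit 2 is used in the analysis to capture the peak TEWL level". Section 5.1b places the TEWL probe over the healed site.

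Section 5.1b also sets the path for ulcers that have not healed "by the end of the 16-week timeline, this visit will mark the participant's Final Study Visit". The items listed for these participants are wound data, a photograph and questionnaires. TEWL is not among them. Section 4 makes entry to Phase B conditional on closure.

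The sample size is set for a multivariable regression "with an expectation of achieving 80% power assuming conditional (fixed X's) model", at a 0.05 significance level with 10 covariates besides biofilm status. On the effect size, section 8 says: "Conservatively, we assumed the effect size to be within small and medium values, equal to 0.03". This gives 264 effective participants. The step to enrolment is: "Assuming 20% loss to follow-up, we need at least 330 participants to be enrolled in the study". Planned enrolment is then raised for a different reason: "Because Study Aim 3.0 needs larger sample, we will enroll more than 330 participants (N=405) for Aims 1-3". The Background says that the proposal "seeks to conduct a fully powered clinical study testing whether DFU with a history of biofilm infection closes with deficient barrier function", and labels this Aim 2.

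**The concern.** Participants reach the analysis only if two things happen: they are not lost, and their ulcer closes within 16 weeks. Section 8 allows for the first only. A participant with an open ulcer at 16 weeks attends Visit 2 and completes the study as planned, so non-closure is not loss to follow-up in the ordinary sense, yet that participant contributes no TEWL value. No closure proportion appears anywhere in the protocol, so a reader cannot tell whether the evaluable number will be reached.

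At stake is the only power statement in the protocol. If fewer than 264 closed ulcers have a Visit 2 TEWL, the Aim 2 comparison has less than 80% power at the chosen effect size, and a null result would be weaker evidence than the text implies.

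**Working it through.** **Inputs from section 8.** Two-sided α = 0.05 (the F test of one coefficient); power 80%; f² = 0.03; one tested predictor plus 10 covariates, so 11 predictors; 264 effective; 20% loss; 330 minimum; 405 planned.

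**Input not in the protocol.** The 16-week closure proportion, c. It is an assumption throughout and is shown as a range.

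**Step 1: reproduce the plan's figures.** Under the fixed-X model, power is P(F′ > F₀.₉₅), where F₀.₉₅ is the central F critical value. F′ is noncentral F with 1 and n − 12 degrees of freedom and noncentrality λ = f² × n.

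- f² = 0.03: smallest n is 264 (power 0.801). Matches.
- f² = 0.02: smallest n is 395 (power 0.801). Matches.
- Inflation for loss: 264/(1 − 0.20) = 330. Matches.

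The arithmetic is correct as far as it goes. What is missing is a factor.

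**Step 2: add closure.** Evaluable n = N × c × (1 − loss). Setting n = 264 gives the closure needed:

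| Enrolled | 20% loss | No other loss |
|---|---|---|
| 330 | 264/(330 × 0.8) = 100% | 264/330 = 80% |
| 405 | 264/(405 × 0.8) = 264/324 = 81.5% | 264/405 = 65.2% |

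The last column also covers the reading in which the 20% was meant to include non-closure: 330 then needs at least 80% closure with nothing else lost.

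**Step 3: power at f² = 0.03 over a range of assumed closure.** n is rounded down.

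| Closure c | 330, 20% loss | 405, 20% loss | 405, no other loss |
|---|---|---|---|
| 90% | n = 237, 75.7% | n = 291, 83.8% | n = 364, 90.9% |
| 80% | n = 211, 70.7% | n = 259, 79.3% | n = 324, 87.5% |
| 70% | n = 184, 64.7% | n = 226, 73.6% | n = 283, 82.7% |
| 60% | n = 158, 58.0% | n = 194, 67.0% | n = 243, 76.7% |
| 50% | n = 132, 50.6% | n = 162, 59.1% | n = 202, 68.8% |

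At 405 enrolled, 20% loss and 50% closure (n = 162), the f² detectable with 80% power is about 0.049 rather than 0.03.

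**Step 4: enrolment needed for 264 evaluable with 20% loss,** 264/(0.8 × c), rounded up: 367 at 90% closure, 413 at 80%, 472 at 70%, 550 at 60%, 660 at 50%.

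**The case against.** The strongest reply is that the study plans 405, not 330, and that 405 may be enough. This stands in part. At 80% closure and 20% loss, power is 79%, which is practically the target. The full 20% may also overstate the loss that matters for Aim 2. The protocol does not split it by phase, and the Visit 2 TEWL is due within 10 days of closure, so dropout during the 12 weeks of Phase B does not reduce the Aim 2 sample. With 10% other loss, the closure needed at 405 is 264/(405 × 0.9) = 264/364.5 = 72.4%. A reader might infer that 405 cannot deliver 80% power; without a closure proportion, the documents do not support that.

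A second reply is that the 20% was meant to cover non-closure. The wording does not say so, and the minimum of 330 would then still need at least 80% closure with no other loss.

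A third is that the general Visit 2 activity list includes TEWL. That measurement is specified over the healed site, and the separate list for unhealed ulcers omits it.

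A reader might also infer that Aim 3 is underpowered, because it too concerns closed ulcers. The protocol states no power, model or recurrence rate for Aim 3 and does not show the calculation behind 405. That calculation may already allow for closure, so a shortfall there cannot be shown. Nor do the documents give figures from which to size any selection bias from analysing closed ulcers only; Aim 2 is openly defined at the closed site. Finally, the protocol does not label TEWL as primary; it is the outcome used for the power calculation.

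**Conclusion.** The point holds for the sample-size statement as written. Three hundred and thirty enrolled gives 80% power only if every retained ulcer closes within 16 weeks, or at least 80% close with no other loss. This follows from the protocol's own visit schedule and needs no outside figure.

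For the planned 405 the shortfall is conditional. It arises if closure is below about 81.5% with 20% loss, or below about 65% with no other loss. With 20% loss, power falls from 84% at 90% closure to 59% at 50%. These figures rest on the plan's f² of 0.03 and its 11-predictor model. Which row of the table applies is unknown, because the protocol gives no closure proportion. The defect is an omitted design assumption, not a slip in the calculation, but it leaves the Background's claim of full power for Aim 2 unsupported as it stands.

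**What to change.** In section 8:

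- Define the effective sample as closed ulcers with a Visit 2 TEWL.
- State the assumed 16-week closure proportion and its basis.
- Replace 330 by 264/(closure × (1 − loss)), saying which losses before Visit 2 the allowance covers.
- Restate the Aim 2 power, or the detectable f², that 405 delivers. If it falls short of 80% at f² = 0.03, qualify the claim of full power in the Background.
- State the Aim 3 basis for 405 on the same closed-ulcer count.

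The blinded looks already planned at 25% and 50% of enrolment are meant to inform recruitment and logistics. They can report the pooled closure proportion and the projected evaluable number without any comparison by biofilm status.

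The cost is rewording and two summary figures at looks that will take place anyway. Restating the power does not itself require more participants. The drawback is that the stated power may become less favourable.
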